### 203 **5.3 Subgroup Analyses**

204 To determine treatment effect heterogeneity on the study outcomes, we will use the same analytical  
205 approach as specified for the primary and secondary outcomes above but include a treatment by  
206 subgroup interaction term in the model. We will report results by the prespecified subgroups,  
207 which consists of the presence or absence of a severe soft tissue injury (defined as severe soft  
208 tissue injury versus no severe soft tissue injury) and the presence or absence of a periarticular  
209 fracture (defined as AO/OTA fracture types 33, 41, 43 and 44 versus all other included fractures).  
210 The results of the subgroup analyses will be reported using a forest plot reporting odds ratios with  
211 95% confidence intervals. These analyses will be approached and reported in accordance with best  
212 practices and guidelines for subgroup analyses. We will use the criteria suggested by  
213 Schandelmaier et al. to guide inferences about the credibility of our subgroup analyses. As  
214 participants may have more than one included fracture representing different subgroups, the

215 analyses will be performed by categorizing participants according to the fracture with the most  
216 severe injury characteristic for each subgroup.

217

218 **5.4 Sensitivity Analyses**

219 We will consider four alternative analysis approaches to evaluate the robustness of our findings,  
220 including alternative definitions of the primary outcome, an as-treated analysis of the primary and  
221 secondary outcomes, a complete case missing data analysis of the primary and secondary  
222 outcomes, and a Bayesian analysis of the primary and secondary outcomes. We will also allow  
223 for post-hoc sensitivity analysis based on information not anticipated in advance.

224

225 *Alternative Definitions of SSI:* To evaluate the robustness of the result, we will consider two  
226 alternative exploratory definitions of SSI: 1) using the confirmatory criteria from the consensus  
227 definition of Fracture-Related Infection (FRI), and 2) expanding the CDC criteria for all types of  
228 SSI to within 1 year of injury.

229

230 Our adjudication of Fracture-Related Infection is defined by the confirmatory criteria outlined in  
231 its 2018 consensus definition. The FRI criteria have been selected as an exploratory outcome  
232 because the CDC criteria have been criticized for failing to adequately account for the complexities  
233 of infections in traumatic fractures. The FRI criteria attempt to improve the ability to detect  
234 infections specifically in fracture patients; however, this definition of FRI has not been fully  
235 validated or widely adopted.

236

237 The confirmatory criteria include the presence of one or more of the following signs/symptoms:

238 1) Fistula, sinus, or wound breakdown (with communication to the bone or the implant).

239 2) Purulent drainage from the wound or presence of pus during surgery.

240 3) Phenotypically indistinguishable pathogens identified by culture from at least two separate

241 deep tissue/implant (including sonication-fluid) specimens taken during an operative

242 intervention. In the case of tissue, multiple specimens (3) should be taken, each with clean

243 instruments (not superficial or sinus tract swabs). In cases of joint effusion arising in a joint

244 adjacent to a fractured bone, fluid samples obtained by sterile puncture may be included as

245 a single sample.

246 4) Presence of microorganisms in deep tissue taken during an operative intervention, as

247 confirmed by histopathological examination using specific staining techniques for bacteria

248 or fungi.

249

250 The second exploratory definition of surgical site infection expands the CDC criteria to a 12-month

251 surveillance period. This outcome will use the same diagnostic CDC reporting criteria for the

252 primary; however, the timeframe for this outcome will be expanded to include all SSIs that occur

253 within 12 months of fracture. Similar to the rationale for using the FRI outcome and the

254 recommendations for a minimum of 12 months follow-up for orthopaedic fracture outcomes, this

255 expanded timeframe will detect infections that occur beyond the standard CDC surveillance

256 reporting periods. This modification of the CDC reporting periods has been used in previous

257 orthopaedic fracture trials.

258

259 *As-Treated Analysis:* One of our sensitivity analyses will be performed on an as-treated population.

260 The as-treated population will include participants from the intention-to-treat population who

261 received one of the two interventions; however, participants will be classified based on the  
262 intervention received at their definitive fracture management surgery. Participants who do not  
263 receive one of the study interventions will be removed from this analysis. Similar to the primary  
264 analysis, we will use mixed effects regression models with a binomial distribution and the same  
265 covariates and correlation structure as the primary model. A more simplified structure will be  
266 considered if we encounter convergence issues with this model.

267

268 *Missing Data:* While we anticipate minimal missing outcome data, we will perform a sensitivity  
269 analysis on the primary and secondary analyses to explore the impact of missing outcome data.  
270 Our sensitivity analysis will be a complete case analysis, including only those patients with a  
271 known status of the outcome being analyzed.

272

273 *Bayesian Analysis:* The Bayesian analyses will be performed using four different priors (neutral  
274 with moderate strength, neutral flat, optimistic with moderate strength, and pessimistic with  
275 moderate strength) defined on a log-odds scale and described below. The neutral priors will be  
276 centered on a log odds of 0 (odds ratio of 1). The neutral flat prior will have a standard deviation  
277 of 100. The optimistic prior will be centered on the estimated effect size of a 0.64 odds ratio (log  
278 odds of -0.45). In contrast, the pessimistic prior is centered on the same effect size but for the  
279 alternative treatment. As suggested by Zampieri et al., the standard deviation of 0.44 was selected  
280 for the moderate strength priors as it allows for a 15% probability of the alternative treatment  
281 benefit in both the optimistic and pessimistic prior. The prior probability of our neutral prior with  
282 a moderate strength distribution implies a 68% chance the estimated effect will be between an odds

[figure not shown]
[figure not shown]
283 ratio of 0.64 and 1.36. The neutral prior with moderate strength will be our preferred prior in this  
 284 sensitivity analysis.

[figure not shown]
285

286 The modeling for the Bayesian analysis will be consistent with our primary analysis. We will use  
 287 a mixed effects regression model with a Bernoulli distribution. The model will include time and  
 288 treatment as fixed effects and use random effects to account for the complex correlation structure.  
 289 The best fitting correlation structure will be determined using information criteria. If we  
 290 experience convergence issues with this model structure, we will transition to a less complex  
 291 model. We will report treatment effects as odds ratios with 95% credible intervals. We will also  
 292 report the probability of treatment benefits of povidone-iodine, with 50% implying no difference  
 293 in the probability of benefit between the two treatment groups.

294

295 **Priors used in the analysis with their interpretation and a visual depiction.**

Prior	Mean	Standard Deviation	Interpretation	Visualization
Neutral with moderate strength	$\text{Log}(1.00) = 0$	0.44	“There is no strong information to suggest the intervention is good or bad in this study population, but we think extreme effect sizes are very unlikely.”	
Neutral flat	$\text{Log}(1.00) = 0$	100	“None of the prior research is relevant to this trial, and we cannot rule out extreme effect sizes.”	

296

297 **5.5 Harms**

298 The number and percentage of patients experiencing serious adverse events will be presented by  
 299 treatment arm. No formal statistical testing will be undertaken.

300

301 **5.6 Statistical Software**

302 The statistical analyses will be performed with SAS, version 9.4 (SAS Institute, Cary, NC) and R  
 303 (R Foundation for Statistical Computing, Vienna, Austria).

304 **6.0 FIGURES AND TABLES**305 **Table 1: Baseline characteristics**

	Iodine Povacrylex in Alcohol (n= XX participants)	Chlorhexidine in Alcohol (n= XX participants)
Age, years, mean (SD)		
Sex, n (%)		
Female		
Male		
Prefer not to answer		
Race or ethnicity, n (%)		
White		
Black		
Central or South American		
Asian		
Indigenous		
Native Hawaiian or Pacific Islander		
Multiracial		
Prefer not to answer		
Body mass index, kg/m  , n (%)		
Underweight (BMI < 18.5)		
Normal weight (18.5 – 24.9)		
Overweight (25 – 29.9)		
Obese (BMI > 30)		
Diabetes, n (%)		
Current smoker, n (%)		
Injury severity score, mean (SD)		
American Society of Anesthesiologist Physical Score, n (%)		
Class I or II		
Class III or higher		
Number of included closed fractures per participant, n (%)		
One		
Two		
Three		

306  
307

308

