4.6.6 Application of Pre-Operative Antiseptic Skin Solutions

Each solution will be applied to the skin and allowed to dry for a minimum of three minutes. While the application and minimum drying time for both study solutions are very similar, local study personnel will provide standardized in-service (training) for orthopaedic surgeons, operating room technicians, and nurses at each participating hospital prior to the initial run-in phase. This training should include reviewing the manufacturers' directions for use to help minimize incorrect application at clinical sites that may not routinely use both solutions. In addition, the manufacturers may also provide demonstration videos and posters for continued refresher training for each solution.

The study protocol will mandate the antiseptic skin solution to be used in each intervention phase (Sections 4.4, 4.6.1, 4.6.2, 4.6.3, and 4.6.4); however, the protocol will remain pragmatic to variability in the actual application of the solutions and other co-intervention steps performed during the entire pre-operative skin preparation process performed in the operating room. Based on individual surgeon preference, this often includes mechanically removing visible dirt or debris with a scrub brush, and/or cleaning the limb with isopropyl alcohol or an antiseptic scrub solution. These additional skin preparation steps will be permitted provided that: 1) the final skin preparation step prior to surgical incision is the application of the allocated antiseptic solution; and, 2) participating surgeons continue to use the same skin preparation co-interventions in both intervention phases. Co-interventions that contain the opposite active ingredient from the current intervention phase (e.g., using a CHG scrub brush during the iodine intervention phase, or conversely, using an iodine scrub during the CHG intervention phase) should be avoided; however, deviations from this recommendation will be permitted to maintain pragmatic *flexibility of delivery* and reflect real-world clinical practice. The details of all operating room antiseptic co-interventions will be documented.

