5.2 Statistical Methods

5.2.1 Analysis Plan Overview

A detailed statistical analysis plan will be published prior to the completion of the trial. The following analysis plan will be conducted independently for the open and closed fracture populations. For each population, the analyses and reporting of the results will follow the CONSORT guidelines for reporting of both pragmatic trials⁴⁷ and cluster-randomized trials.⁴⁸ The process of participant enrollment and flow throughout the study will be summarized using a flow-diagram. Participant demographics and baseline outcome variables will be summarized using descriptive summary measures expressed as mean (standard deviation) or median (interquartile range) for continuous variables depending on the distribution, and number (percent) for categorical variables.⁴⁹ An ITT principle will be adopted to analyze all outcomes and the unit of analysis will be the individual participants. Missing data will be assumed to be missing at random and will be handled with multiple imputation.^{50,51}

The primary analysis will compare the treatment groups using the SSI outcome and the secondary analysis will compare the unplanned fracture-related reoperation outcome. The secondary comparison will be conducted in accordance with best practice guidelines for secondary analyses. For all models, the results will be expressed as relative measure of effect (odds, risk, or hazard ratios) and corresponding two-sided 95% confidence intervals.

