28 All study outcomes will be tested for superiority.

29

30 **2.5 Interim Analysis and Stopping Guidance**

31 PREPARE Closed does not have a planned interim analysis. However, the trial's Data and Safety  
32 Monitoring Committee reviews the reporting of serious adverse events biannually and can  
33 recommend early stopping if safety concerns are identified.

34

35 **2.6 Timing of Outcome Assessments**

36 Research personnel will contact study participants at 6 weeks, 3 months, 6 months, 9 months, and  
37 12 months after their fracture. Our primary outcome will be surgical site infection (SSI) and it will  
38 be assessed at 30 days (superficial infections) and at 90 days (deep and organ space infections)  
39 after definitive fracture management surgery. The secondary outcome will be occurrence of an  
40 unplanned fracture-related reoperation within 12 months of the fracture. Additional time points  
41 will be used for our planned sensitivity analyses.

42

43

44

45 **3.0 STATISTICAL PRINCIPLES**

46 **3.1 Confidence Intervals and P-Values**

47 All statistical tests will be two-sided and performed using a 5% significance level. We will report  
48 all confidence intervals as 95% and two-sided. All results will be expressed as odds ratios produced  
49 by analyses described in section 5.2. Interaction p-values will be provided for the subgroup  
50 analyses. We will not adjust for multiple testing, and all sensitivity analyses and secondary results  
51 will be interpreted as exploratory.

52

53 **3.2 Adherence and Protocol Deviations**

54 Adherence will be assessed at the definitive fracture surgery for each participant and will be binary  
55 in its definition. We will report adherence as the number and percentage of participants who  
56 received the allocated intervention at their definitive fracture management surgery. If the  
57 participant has multiple closed fractures and received the non-allocated treatment at the definitive  
58 fracture management surgery for any of their closed fractures, we will consider them non-adherent.  
59 We will also tabulate the reasons for non-adherence. The adherence percentages and reasons for  
60 non-adherence will be reported by treatment arm.

61

62 Our rationale for defining adherence based solely on the antiseptic solution used during the  
63 definitive fracture management surgery is that the vast majority of closed fractures do not require  

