64 staged surgical management and that the definitive fracture management surgery involves the final  
65 implantation of the surgical fixation hardware, when it is most susceptible to bacterial  
66 contamination and biofilm development.

67

68 **3.3 Analysis Populations**

69 *Intention-to-Treat*: Our primary analysis will use the intention-to-treat approach and will include  
70 all enrolled patients in the treatment groups to which their cluster was allocated at the time of their  
71 first fracture management surgery.

72

73 *As-Treated*: One of our sensitivity analyses will be performed on an as-treated population (see  
74 Section 5.4). The as-treated population will include participants from the intention-to-treat  
75 population but classified based on the intervention received at their definitive fracture management  
76 surgery. Participants who do not receive one of the two study interventions will be excluded from  
77 this analysis. This approach for defining the as-treated treatment groups is a simpler adaptation of  
78 what was initially proposed in the protocol. This final approach was selected to be consistent with  
79 the classification of adherence outlined above.

80

81

82 **4.0 TRIAL POPULATION**

83 **4.1 Cluster Screening and Eligibility**

84 Prior to commencing the trial, the investigators solicited orthopaedic surgery practices treating  
85 patients with closed fracture(s) of the lower extremity or pelvis in hospitals in the United States  
86 and Canada to participate in the trial. All potential clusters completed a feasibility questionnaire  
87 prior to initiating start-up activities. To be included in the trial, each cluster had to demonstrate: 1)  
88 adequate research personnel infrastructure to manage the study, 2) adequate fracture patient  
89 volume to complete enrolment within the study timeline, 3) a commitment from all surgeons to  
90 adhere to the assigned interventions, and 4) the ability to procure both study interventions. All  
91 hospitals started with a run-in phase of at least 1 month to demonstrate that they could adhere to  
92 the trial protocol prior to commencing the study.

93

94 We will report the number of clusters (orthopaedic practices) screened, included, and excluded in  
95 a flow diagram. The number of clusters excluded by reason has been reported previously. Cluster  
96 randomization allocation will be included in the flow diagram, and adherence with treatment  

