97 allocation during the run-in period by cluster will be summarized using percentages.

98

99 **4.2 Patient Screening and Eligibility**

100 All patients 18 years of age or older who present to a recruiting hospital for treatment of a closed  
101 fracture(s) of the lower extremity or pelvis will be screened by a research staff member for  
102 participation within 6 weeks of their fracture. Eligible patients must receive surgical incision (i.e.,  
103 for fracture reduction or implant insertion), and the closed fracture(s) must be managed definitively  
104 with a surgical implant (e.g., internal fixation, external fixation, joint prosthesis, etc.). Written

105 informed consent is required for study enrollment to permit the clinical follow-up of study  
106 participants. However, our institutional review board did not require informed consent to occur  
107 prior to the study treatment, given the urgent nature of the surgery and the predetermination of the  
108 two commonly used interventions with cluster-crossover design. The patients, treating clinicians,  
109 and research team members at the participating sites are unmasked to the treatment allocation.

110

111 The number of patients screened, included, and excluded will be presented in a flow diagram  
112 (**Figure 1**). The figure will consist of the number of patients who were eligible, ineligible, and  
113 enrolled. In addition, the number of patients excluded by reason will be summarized. We will also  
114 list the number of participants who were enrolled and subsequently deemed ineligible by the  
115 Central Adjudication Committee by treatment group and overall. Participants deemed ineligible  
116 by a central adjudication committee blinded to the treatment will not be included in any analysis,  
117 as per the guidance of Fergusson et al.

118

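### Both SAPs plan one serious-adverse-event summary with no defined harms population: the ineligibility rule removes exposed patients from it, and infection and reoperation events can mask or offset an excess of solution-related reactions

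*SAP*

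**What the plan says.** Section 5.5 has the same two sentences in the Closed and Open SAPs. "The number and percentage of patients experiencing serious adverse events will be presented by" and then "treatment arm. No formal statistical testing will be undertaken". Nothing is said about type, relatedness or the set of participants counted, and Tables 1 to 3 of either SAP have no SAE row.

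The surrounding rules are these.

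- **Exclusion.** SAP 4.2 provides that participants ruled ineligible "by a central adjudication committee blinded to the treatment will not be included in any analysis". Their number is listed by treatment group; their SAEs are not mentioned.
- **Population.** SAP 3.3 ties allocation to one analysis: "Our primary analysis will use the intention-to-treat approach and will include" all enrolled patients by the cluster's allocation at first surgery. Protocol 5.2.1 is broader: "An ITT principle will be adopted to analyze all outcomes". No safety set is defined.
- **As-treated analysis.** SAP 5.4 lists the sensitivity analyses, "including alternative definitions of the primary outcome, an as-treated analysis of the primary and" secondary outcomes. Harms are not among them.
- **SAE definition.** Protocol 7.5.1 counts any adverse event that leads to or lengthens a hospital stay, with no carve-out for study outcomes.
- **Safety handling outside the SAPs.** Protocol 7.5.4 requires immediate SAE reporting, a causality assessment, regulatory reporting of serious unexpected reactions and central tracking of non-serious ones. Protocol 7.5.6 gives the Data and Safety Monitoring Committee SAE summaries and listings.
- **Deaths.** SAP 4.3 tabulates them, without saying whether by arm.

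**The concern.** The trial compares two routine products, and a reader of its report will want to know whether one causes more harm. Two features of the plan make the harms figure a poor answer.

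First, a blinded ineligibility ruling is a defensible reason to leave a participant out of the effectiveness comparison. It is no reason to leave out an observed harm. Consent may follow surgery (Protocol 7.2), so a participant may already have been exposed when ruled ineligible.

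Second, the SAE count mixes two things. A deep infection or unplanned reoperation that brings the patient back to hospital is both an efficacy event and an SAE. Protocol 1.1 itself cites research in which fracture patients with an SSI typically had at least two further operations and a median of 14 extra hospital days, so overlap is to be expected. If iodine prevents infections, its SAE count falls for that reason, and this fall can cover a rise in serious reactions to it. An excess of reactions on chlorhexidine would instead look like part of its infection excess.

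**Working it through.** **Denominators.** The harms sections state no figure, so the only plan figures used are the sample sizes. Protocol Table 6: 5,700 × 1.1 = 6,270, rounded up to a multiple of 20 = 6,280. Table 5: 1,400 × 1.1 = 1,540. Equal split: 3,140 and 770 per arm. The ordinary two-proportion formula (two-sided 0.05, 80% power) gives 5,798 for the Closed odds ratio of 0.64, within 2% of 5,700. For Open it gives 1,516 to 1,524 against 1,400, which does not match; that is a separate matter, and only the enrolment minimum is used here.

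**Masking (illustration).** The documents give no SAE or reaction rate. Assume 10–20% of patients per arm have an SAE for other reasons. For Open this brackets the 13.2% reoperation incidence that Protocol 1.1 quotes from an earlier open-fracture trial; for Closed there is no such anchor. Suppose ten more patients in one arm have a serious solution-related reaction, against none in the other.

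- Own row, 10 v 0: with equal arms the two-sided Fisher p is close to 2 × 0.5^10 = 0.00195; the exact value rounds to 0.002 in both trials.
- Inside the all-SAE count, Closed: 324 v 314 of 3,140 (10%), p = 0.71; 638 v 628 (20%), p = 0.78.
- Inside the all-SAE count, Open: 87 v 77 of 770 (10%), p = 0.46; 164 v 154 (20%), p = 0.57.
- An excess of 20 inside the count: p = 0.43 to 0.55 (Closed), 0.13 to 0.24 (Open).
- 95% half-width of the all-SAE difference, in patients, = 1.96 × n × √(2b(1−b)/n), with b the background: 47 to 62 (Closed), 23 to 31 (Open).

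The p-values only gauge visibility. The SAPs plan no test of harms, and these calculations ignore clustering.

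**Offset at the planned effect.** Inputs from Protocol 5.1: chlorhexidine SSI risk 3.5% (Closed) and 12.5% (Open), risk ratio 0.65.

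- Closed: 3,140 × 0.035 = 109.9 v 71.4 on iodine, 38.5 fewer.
- Open: 770 × 0.125 = 96.3 v 62.6, 33.7 fewer.

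Let s be the share of SSIs that are also SAEs (assumed) and let iodine have 20 more patients with serious reactions. Net SAE difference, iodine minus chlorhexidine, = 20 − s × (SSIs prevented):

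| s | Closed | Open |
|---|---|---|
| 0.25 | +10.4 | +11.6 |
| 0.5 | +0.8 | +3.2 |
| 1.0 | −18.5 | −13.7 |

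**Exclusion.** The documents give no ineligibility rate. At an assumed 1–3%, 1,540 × 0.01 to 0.03 = 15 to 46 (Open) and 6,280 × 0.01 to 0.03 = 63 to 188 (Closed) participants leave the harms report. Not all of them need have been exposed.

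**Attribution.** If a fraction a of each arm receives the other solution, a fraction a of a solution's reactions is counted in the wrong arm, and a contrast of 10 becomes 10 × (1 − 2a). At a = 2–5%, 0.2 to 0.5 in 10 are misplaced (contrast 9.6 to 9.0). At 10%, 10 v 0 becomes 9 v 1.

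**The case against.** **The text does not forbid a breakdown.** True: section 5.5 neither prescribes a single row nor rules out more. But it commits to nothing further, and a statistician following it would have no instruction to separate anything.

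**Outcome events are shown elsewhere.** Table 3 of each SAP gives SSI by depth and reoperation by cause, by arm. That helps, but a reader cannot subtract those events from a patient-level SAE percentage without knowing the overlap.

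**The size of the overlap and exclusion is assumed.** This stands. The definition shows that overlap exists, not how large it is. Some ineligible participants will never have received a study solution, since a medical contraindication to the allocated one is itself an exclusion criterion. Nor do the documents say that follow-up continues after an ineligibility ruling.

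**A reader might infer that harm is lost to the trial.** The documents do not support this. Causality assessment, regulatory reporting and committee review of SAE listings continue whatever the SAP tabulates, and deaths are counted separately.

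**A reader might also infer that reactions are materially charged to the wrong solution.** This is not supported either. Section 5.5 does not say allocated arm. That is the best reading, because SAP 3.2 says that "non-adherence will be reported by treatment arm", which makes sense only for allocation. But the effect is small at 2–5% non-adherence, and the 90% level in Protocol 4.6.5 is a site-level trigger for possible withdrawal, not an expected rate. Some non-adherent patients may receive neither solution. Scrubs with the opposite ingredient are discouraged, but "deviations from this recommendation will be permitted to maintain pragmatic" flexibility (Protocol 4.6.6); classifying by study solution received would not capture them.

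**Conclusion.** The concern holds in limited form, identically for both SAPs. As written, section 4.2 takes exposed participants out of the harms report; this assumes only that a descriptive SAE table counts as an analysis, and no exception is stated. Section 5.5 offers a single SAE percentage that partly repeats the efficacy results. At the assumed backgrounds, an excess of ten serious reactions that is plain in its own row is indistinguishable from noise in the pooled count. At the planned effect, an excess of 20 on iodine is roughly cancelled if half of SSIs are SAEs, and the sign reverses if all are. Masking is the main weakness. The loss through exclusion cannot be sized from the documents, and wrong-arm counting is minor. It would go too far to say that the report could not address comparative harm at all; it would address it poorly. The conclusion concerns the planned trial report, not safety oversight.

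**What to change.** In both SAPs:

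1. **Section 4.2:** limit the exclusion of participants ruled ineligible to the SSI and reoperation analyses. Define the harms set as all consented participants exposed to a study solution, using whatever SAEs were recorded for those later ruled ineligible.
2. **Section 5.5:** report by arm (a) all SAEs, (b) SAEs other than adjudicated SSI or unplanned reoperation, and (c) serious reactions judged related to the solution under Protocol 7.5.4. Give the death tabulation already planned in 4.3 by arm.
3. **Section 5.5:** state that treatment arm means the allocated arm, and add a supplementary table by solution received at definitive surgery, following the SAP's existing as-treated rule.

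The cost is wording and a few table rows. Rows (a) and (b) need SAE and adjudication records that the protocol already requires. Row (c) needs a check first: Protocol 7.5.4 describes causality assessment within regulatory reporting and does not show that every SAE has a recorded judgement. There are two downsides. Harms and effectiveness will have different denominators to explain, and relatedness judgements that involve unmasked site staff must be read with caution.
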